C. Describe steps to be taken to minimize risks. Include a description of your efforts to arrange for care or referral for participants who may need it.

Clients: Every effort will be made to protect the identity and confidentiality of participants and contact information will always be kept in a secure location separate from other study materials. Research Assistants will make it clear that participants may refuse to answer questions and may stop the interview at any time.

Providers and Facility Managers: The study team will make efforts to ensure that confidential information and any records linking individuals to their responses are protected. Provider responses and results of the quality assessments will be presented at an aggregate level and individual results will not be shared with facilities or with stakeholders. While data from the provider quality assessments may be used to assess overall facility quality, information identifying specific facilities will not be included in analysis or dissemination. Data collected from KIIs will be held in a secure location and identifiers will not be collected.

Policy Makers and Community Influencers: As with other participant groups, the identities of participating community influencers will be confidential. Data collected from KIIs will be held in a secure location and identifiers will not be collected.

D. Describe the research burden for participants, including time, inconvenience, out of pocket costs, etc.

For all participants, the primary burden is time: 90 minutes per FGD (up to one per participant) and KIIs (up to one per participant) and approximately 30-45 minutes per interview (up to three per participant). However, especially for FGD and KII participants, there are potential inconveniences and out-of-pockets expenses tied to returning to the pre-identified interview/FGD location.

E. Describe how participant privacy will be protected during data collection if sensitive questions are included in interviews.

Clients: All data collection from clients will be conducted in private locations agreed upon by the interviewer and the participant. FGDs will take place in a pre-arranged private location. If the participant is accompanied to the location, the person accompanying them will not be permitted into the FGD location while discussions are ongoing. Client Interviews will ideally take place at a private location in the facility, designated by facility staff in collaboration with the study team. Anyone accompanying the client for the ANC visit from which she is recruited will be asked to wait outside the interview location during the interview. If a client would like to participate but is unable to sit with the data collector at the facility, the interviewer and client will agree on a time and private place to meet to conduct the interview. KIIs will ideally take place immediately following the 6-month postabortion interview, also ideally in a private location at the facility, but will be held at a designated time-place if needed.

Providers and Facility Managers: Interviews will be conducted in a private location agreed upon by the participant and the interviewer. If the location is in the facility, extra efforts will be taken to ensure that the location has audio and visual privacy in order to assure the provider of the confidentiality of responses.

Policy Makers and Community Influencers: We do not anticipate questions asked during KIIs with Community Influencers to be sensitive. However, steps will still be taken to ensure privacy during interviews, which will be conducted in a private location agreed upon by the participant and the interviewer.

VIII. Direct Personal and Social Benefits:

A. Describe any potential direct benefits the study offers to participants (“payment” for participation is not a direct personal benefit).

Providers and clients will not directly benefit from participating in this assessment. Clients will not be offered any money or gift for participating in the study.

Describe potential societal benefits likely to derive from the research, including value of knowledge learned. Potential benefits we anticipate include the fact that the results of this study will generate crucial learning about implementing quality immediate postpregnancy FP counseling and service in low-resource settings, to be applied widely now that revised MEC are in place.

IX. Payment:

A. Describe the form, amount, and schedule of payment to participants. Reimbursement for travel or other expenses is not “payment,” and if the study will reimburse, explain.

Participants will not receive any payment or compensation for participating in the study. No payment will be made to any health facility, nor will any provider or administrator receive any payment. However, travel costs may be reimbursed for FGD and KII participants without a receipt for up to \$10 USD. If the amount is greater than \$10, a receipt will be requested.

B. Include the possible total remuneration and any consequences for not completing all phases of the research.

As travel costs will be reimbursed for all FGD, IDI and KII participants without a receipt for up to \$10 USD, the total travel reimbursement is up to \$20 (two KIIs) per KII participant and \$10 (one per FGD or IDI participant). If the amount is greater than \$10, a receipt will be requested.

X. Study Management:

A. Oversight Plan:

1. Describe how the study will be managed.

The study will be managed by the PI ([name]) and co-investigators on this study. Additionally, in-country PIs will be [name] for Kenya and [name] for Indonesia.

2. What are the qualifications of study personnel managing the project?

[name], MBA, MHS is the Project Director for the Postpregnancy Family Planning Choices project at Jhpiego and has over 10 years of research experience in international settings. She will provide overall oversight in the implementation of all aspects of the study in both Kenya and Indonesia.

Co-investigators include [name] from Jhpiego/Kenya who will be the Kenya Team Leader managing the study implementation in Kenya and [name] from Jhpiego/Indonesia who will be the Indonesia Team Leader managing the study implementation in Indonesia. Both of these co-investigators have previous experience managing research studies in their countries and have programmatic knowledge and management skills to lead the study implementation according to this protocol.

Table 7: Roles Investigators

Name of Investigator	Position/ Role	Specific responsibility
[name], Jhpiego	Principal Investigator	Overall study implementation oversight in Kenya and Indonesia
[name], Jhpiego Kenya	Senior MER Advisor, Kenya	Lead-in country Investigator
[name], Jhpiego Indonesia	Senior MER Advisor, Indonesia	Lead-in country Investigator

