Focus Group Discussions (FGDs)	From Each County/District: Women 6 to 12 months postpartum 1. (2) groups of 8 adult public facility acceptors 2. (2) groups of 8 adolescent public facility acceptors 3. (2) groups of 8 adult private facility acceptors 4. (2) groups of 8 adolescent private facility acceptors 5. (2) groups of 8 public non-acceptors 6. (2) groups of 8 private non-acceptors Total = 96 participants per arm per country per year	Identify social, cultural, contextual, economic and age- and gender-related factors affecting women's perceptions of, access to and use of FP	Year two	Postpartum Clients: 6-12 months postpartum
In-Depth Interviews	Postabortion women who had planned to receive a FP method did not receive a FP method during the immediate postabortion period	Identify social, cultural, contextual, economic and age- and gender-related reasons women did not receive an immediate postabortion family planning method		Postabortion clients: 6-month follow-up
Facility Audit	Facilities, facility in-charges	Identify facility-level supply-side barriers to accessing and utilizing PPFP	Year one (baseline), year two (midline), year three (endline)	

B. Provide a sample size and a justification as to how you arrived at that number. If you use screening procedures to arrive at a final sample a table may be helpful.

Health facilities selected for study implementation, from where participants will be recruited, will have met the following criteria:

- Site where provider(s) trained in LARC methods exist (or in Kenya: where we can train them);
- Facility birth rate at least 50 deliveries per month;
- Programmatically feasible (distance, etc.);
- The health facility is within or serves the study region;
- The facility is legally registered and current in its registration;
- Either public, or private for-profit (Indigenous owned, tax paying) facilities

This study will collect data from individuals recruited at selected facilities through both qualitative and quantitative methods. An overview of the total sample to be included is outlined in table 3.

Table 3: Sample size of recruited study participants

	Kenya Public Facilities	Kenya Private Facilities	Kenya Ministry of Health and Policy Makers	Kenya Community Influencers	Indonesia Public Facilities	Indonesia Private Facilities	Indonesia Ministry of Health and Policy Makers	Indonesia Community Influencers	Total sample
Key Informant Interview	3	3	3	3	3	3	3	3	24
<hr/>									

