	Kenya Public Facilities Intervention	Kenya Public Facilities Control	Kenya Private Facilities Intervention	Kenya Private Facilities Control	Indonesia Public Facilities Intervention	Indonesia Public Facilities Control	Indonesia Private Facilities Intervention	Indonesia Private Facilities Control	Total sample
Postpartum Client Interview	1803	1803	451	451	1715	1715	429	429	8796
Postabortion Client Interview	174		69		161		82		486
TOTAL SAMPLE SIZE									9282
Focus Group Discussions	48	48	48	48	48	48	48	48	384
Postabortion In-Depth Interviews	6	6	2	2	6	6	2	2	32
Total FGD and Postabortion Qualitative Interviews (Participants from Postpartum and Postabortion Client Interviews)									416
TOTAL SAMPLE SIZE									9282

More detail about the sample sizes for each method is outlined in the following section, categorized by data collection method or population of interest.

Qualitative Interviews (Focus Group Discussions, Initial Key Informant Interviews, In-Depth Interviews):

In each country, 12 initial Key Informant Interviews (KIs) will be conducted at baseline and again at the end of the study.

In each county/district, 12 FGDs will be conducted with participants 6 to 12 months postpartum. Two FGDs will take place for each of the following groups:

- 2 FGDs of 8 adult public facility acceptors
- 2 FGDs of 8 adolescent public facility acceptors
- 2 FGDs of 8 adult private facility acceptors
- 2 FGDs of 8 adolescent private facility acceptors
- 2 FGDs of 8 public non-acceptors
- 2 FGDs of 8 private non-acceptors

Each FGD will be comprised of eight participants as a group size of six to twelve has been advocated for logistical purposes as well as to ensure the breadth of responses required [9][10][11][13][14].

Additionally, 16 in-depth interviews per country will be conducted with postabortion clients who did not receive any modern FP method at the immediate postabortion period. We anticipate that a sample size of 16 will allow for data saturation.

Our sampling strategy for qualitative interviews will help to achieve saturation of themes for our domain of interest, and will also provide a sufficient amount of data to compare across regions and countries.

Client Interviews:

All postpartum and postabortion participants will complete an interviewer-administered survey at each study visit. In calculating our sample sizes for this study, we make the following assumptions:

Table 4: Sample Size Calculations, Postpartum

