	Sample Size, assuming 30% attrition, 10% refusal	Design Effect (2.5) and Cluster Size Adjusted Sample Size Per Arm	Sample size per arm (80% Public, 20% Private)	Total per Country (2 arms)
Kenya Public	721	2254	1803	4508
Kenya Private			451	
Indonesia Public	686	2144	1715	4288
Indonesia Private			429	

Table 5: Sample Size Calculations, Postabortion

Study Arm	Base sample size of post-abortion clients (per arm – assuming 50% uptake and 40% continuation at 6-months)	Attrition Adjusted Sample Size per arm (estimating 20% attrition)
Kenya Intervention	194	243
Indonesia Intervention	194	243
Total		486

Separate sample sizes have been calculated for Indonesia and Kenya. Estimates aim to measure a difference in the six-month postpartum acceptance of long-acting reversible and permanent methods (LARC+PMs) by postpartum women seeking services at comparison and intervention facilities. Sample size calculations for both countries are based on a 95% two-sided confidence interval with 80% power. The sample size was calculated in two stages. First, we calculated the sample size for simple random sampling. Next, the sample size was adjusted to take into account a design effect of 2.5 in order to adjust for within-cluster correlation and non-response.

In Indonesia, we used an analysis of PPPF utilization from the 2012 Demographic and Health Survey (DHS) and conversations with the My Choice project team (My Choice is a Bill and Melinda Gates Foundation-supported project currently strengthening family planning services at facilities in Indonesia) to estimate a baseline LARC+PM use of approximately 10% at six months postpartum. In Kenya, we analyzed FP method use among a subset of 3,857 women with a child under one year interviewed during the 2014 Kenya DHS to estimate a LARC+PM use rate of 6% at six months postpartum. Sample sizes were calculated to measure a change from 10% to 15% in Indonesia and from 6% to 10% in Kenya at intervention facilities over the course of the study. We have further estimated a need for 20% of the sample to be recruited from private facilities in order to effectively measure changes in both types of facilities. An overview of the sample size for each country is shown in Table 4. This table displays the required number of post-pregnancy women to be recruited per arm to measure the change in LARC+PM use post-pregnancy from 10% to 15% in Indonesia and from 6% to 10% in Kenya at the end of the study.

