Facility Audits: Data Analysis: Mapping of facilities will be visually analyzed to provide further understanding of structural issues that may influence perceptions and key behaviors. We will also utilize multi-level data analysis to explore the feasibility of IPPI using STATA. Select data from the client interviews will be combined with key facility level indicators for a multilevel analysis of the factors affecting intention to use and receipt of immediate post-pregnancy family planning methods.

[figure not shown]
Furthermore, triangulation across methods will help to ensure quality of study findings and offer opportunities for deeper insights into the study concepts [12]. Observations will also be collated with qualitative analysis results and used to strengthen themes identified through key informant data. In addition, a team approach to data analysis will be employed where different researchers provide feedback on emerging interpretations and analysis and check developing categories and concepts back against the original data. In this way, an “audit trail” will be used to help ensure trustworthiness of findings and gather input from multiple investigators [12].

5. Answer the following if they are relevant to your study design:

A. If the study has different arms, explain the process for assigning participants (intervention/control, case/control), including the sequence and timing of the assignment.

The study will employ a quasi-experimental mixed-method design; both quantitative and qualitative data will be collected at multiple time points. In coordination with the MOH, we will first identify an “intervention area” and a “control area” at County-level in Kenya and an “intervention area” and a “control area” at District-level in Indonesia. Within the “intervention areas,” we will identify intervention facility sites (six in Kenya and four in Indonesia) and match them with an equal number of control facility sites from the “control areas,” based on a list of predetermined criteria (e.g., service statistics and client demographics).

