All facilities in the “intervention area” will receive all facility level training and support interventions at the beginning of and throughout the study data collection period, while all facilities in the “control area” will be afforded the benefits of the interventions in a phased manner; in the last 6 months of the study timeline, after data collection activities are completed. This is demonstrated in the following graphic:

*Note: exact number of implementation sites TBD

- B. If human biospecimens (blood, urine, saliva, etc.) will be collected, provide details about who will collect the specimen, the volume (ml) and frequency of collection, how the specimen will be used, stored, identified, and disposed of when the study is over. If specimens will be collected for use in future research (beyond this study), complete the "Biospecimen Repository" section below.
N/A
- C. If genetic/genomic analyses are planned, address whether the data will be contributed to a GWAS or other large dataset. Address returning unanticipated incidental genetic findings to study participants.
N/A
- D. If clinical or laboratory work will be performed at JHU/JHH, provide the JH Biosafety Registration Number.
N/A
- E. If you will perform investigational or standard diagnostic laboratory tests using human samples or data, clarify whether the tests are validated and/or the lab is certified (for example is CLIA certified in the U.S.). Explain the failure rate and under what circumstances you will repeat a test. For all human testing (biomedical, psychological, educational, etc.), clarify your plans for reporting test results to participants and/or to their families or clinicians. Address returning unanticipated incidental findings to study participants.
N/A
- F. If your study involves medical, pharmaceutical or other therapeutic intervention, provide the following information:
 - a. Will the study staff be blind to participant intervention status?
N/A

- b. Will participants receive standard care or have current therapy stopped?
N/A
- c. Will you use a placebo or non-treatment group, and is that justifiable?
N/A
- d. Explain when you may remove a participant from the study.
N/A
- e. What happens to participants on study intervention when the study ends?
N/A
- f. Describe the process for referring participants to care outside the study, if needed.
N/A

VI. Data Security and Confidentiality Protections:

A. Personally Identifiable Information (PII):

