E. **Facility Audits Data Analysis:** Mapping of facilities will be visually analyzed to provide further understanding of structural issues that may influence perceptions and key behaviors. Aggregated country and district/county data from the baseline audits will be used to inform final program intervention design where possible. Additionally, select data from the client interviews will be combined with key facility level indicators for a **multilevel analysis** of the factors affecting intention to use and receipt of immediate post-pregnancy family planning methods, and to assess the overall success of the program.

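### With one county or district per arm, area and arm coincide, so the stated 95% confidence and 80% power hold only for the two areas compared and leave out area-to-area variation

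*Protocol*

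**What the plan says.** Protocol V.C.5.A identifies, with the Ministry of Health, one intervention and one control area per country: "we will first identify an “intervention area” and a “control area” at County-level in Kenya". Indonesia follows the same scheme, with districts in place of counties. Study facilities are picked within the intervention area and matched to facilities in the control area on criteria such as service statistics and client demographics. Allocation is area-wide: "All facilities in the “intervention area” will receive all facility level training and support interventions".

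The focus-group counts confirm one area per arm. III.B states: "In each county/district, 12 FGDs will be conducted with participants 6 to 12 months postpartum". Table 2 gives: "Total = 96 participants per arm per country per year".

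For the postpartum sample size, III.B says: "Sample size calculations for both countries are based on a 95% two-sided confidence interval with 80% power". The simple-random-sampling n is then inflated: "the sample size was adjusted to take into account a design effect of 2.5 in order to adjust for within-cluster correlation and non-response". No ICC is given and the cluster is not named.

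SAP A compares arms by bivariate and multivariable logistic regression, with no clustering term stated for that comparison. The multilevel model in Protocol V.C.4 and SAP A and E joins client data to facility indicators to study determinants of intention and receipt. SAP E adds a further use: "and to assess the overall success of the program". No area-level term, area variance or related limitation appears.

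**The concern.** Women and facilities in one county or district share its supply chain, policy, staffing and client mix. Two such areas would differ somewhat in uptake with no program at all. A standard error built from women, or from women within facilities, describes how well each area's rate is known. It does not describe how far two areas differ for other reasons.

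An interval or p-value from the planned analysis could therefore be read as evidence on the program at the stated error rates, when it is evidence on a difference between two places. This is separate from facility clustering: a correct facility-level standard error would leave the gap in place. The areas are also chosen purposively, so the limit is one of confounding as well as of variance.

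**Working it through.** **1. Areas per arm.** 12 groups × 8 women = 96 per county or district (III.B). Table 2 gives 96 per arm per country, and Table 3 gives 48 public + 48 private = 96 per arm. So there is one area per arm. Degrees of freedom for area variance within arms: 2 areas − 2 arms = 0.

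**2. The plan's own figure.** Inputs from III.B: 6% v 10% (Kenya), 10% v 15% (Indonesia), two-sided 5%, 80% power. With p̄ the mean of the two rates,

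n = [1.96√(2p̄q̄) + 0.8416√(p1q1 + p2q2)]² / (p2 − p1)²

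- Kenya: [1.96√0.1472 + 0.8416√0.1464]² / 0.0016 = 721 (Table 4: 721).
- Indonesia: [1.96√0.21875 + 0.8416√0.2175]² / 0.0025 = 686 (Table 4: 686).

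Multiplying by 2.5 and dividing by 0.8 for the public share gives about 2,253 and 2,144 per arm (Table 4: 2,254 and 2,144). Nothing in this chain is an identified area variance.

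**3. What 2.5 would mean if the cluster were the area.** ICC = 1.5/(m − 1) = 1.5/2,253 = 0.00067 (Kenya) and 1.5/2,143 = 0.00070 (Indonesia). As an SD, √(ICC × p̄q̄) is about 0.7 and 0.9 points. The plan does not justify so small a value, and there are still 0 degrees of freedom to check it.

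**4. Effect of an assumed residual area SD.** The documents give no area SD, so a range is shown. The variance of an arm difference is SE² + 2·SD².

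SE under no effect, at the control rate: √(2 × 0.06 × 0.94/721) = 1.25 points (Kenya); √(2 × 0.10 × 0.90/686) = 1.62 points (Indonesia).

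False-positive rate = 2[1 − Φ(1.96·SE0/√(SE0² + 2·SD²))]:

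| Assumed area SD | Kenya | Indonesia |
|---|---|---|
| 0 | 5% | 5% |
| 0.5 points | 9% | 7% |
| 1 point | 19% | 14% |
| 2 points | 43% | 33% |

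**5. Power with area variance counted.** SE at the planned effect: √(0.1464/721) = 1.42 points; √(0.2175/686) = 1.78 points. Power = Φ(d/√(SE² + 2·SD²) − 1.96).

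- SD 0: about 80% in both countries, as stated.
- SD 1 point, Kenya: Φ(4/2.01 − 1.96) = 51%.
- SD 1 point, Indonesia: Φ(5/2.27 − 1.96) = 59%.

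**6. Break-even SD at the planned effect.** Solve 1.96√(SE² + 2·SD²) = d, so SD = √{[(d/1.96)² − SE²]/2}.

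- Kenya: √[(4.165 − 2.031)/2] = 1.03 points.
- Indonesia: √[(6.508 − 3.171)/2] = 1.29 points.

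**7. More women do not help.** With unlimited women per area, SE is 0 and 80% power needs SD ≤ d/(2.8016·√2) = 1.01 points (Kenya) or 1.26 points (Indonesia).

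**The case against.** Several counter-arguments have force.

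- **Matching and adjustment.** Facilities are matched and multivariable regression is planned, so the relevant SD is what remains afterwards and may be smaller than the raw one. This stands as a limit on size. It does not restore the stated error rates, because the residual cannot be estimated. Client recruitment (months 6–30) also follows intervention training (months 4–6), so there is no pre-intervention client survey, and difference-in-difference is planned only for supervision records.
- **The design is declared quasi-experimental, and impact is secondary.** True: the primary question concerns determinants, and the regression is described as exploring arm differences. But the label concerns the lack of randomisation. It does not tell a reader that the 95% and 80% in III.B assume no area variance.
- **Purposive areas are a confounding question.** This is fair. A false-positive rate over hypothetical areas is one way to express the limit, and confounding is another.
- **The effective n is debatable.** Recruited n divided by 2.5 is 902 and 858. After the 30% attrition and 10% refusal in Table 4 (× 0.7 × 0.9) it is about 568 and 540. At SD 1 point the false-positive rates become about 22% and 16%, or about 17% and 12%. The pattern is unchanged.

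A reader might infer that the plan treats facilities as the independent units. III.B never names the cluster behind 2.5, and the arm comparison in SAP A is logistic regression, not the multilevel model. The point does not depend on which cluster was meant.

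**Conclusion.** The point holds in a limited form. Arm is assigned by one area per country, and neither the sample size nor the analysis carries an identifiable area variance. The stated 95% confidence and 80% power are therefore conditional on the two areas compared. For a program effect they require residual area variance near zero.

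The size is illustrative. It rests on an assumed area SD, on the plan's base n, on normal approximations, and on treating the areas as draws from a wider set.

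A reader might go further and take a significant difference to be the expected result of ordinary area differences. The figures do not show that: over SDs of 0.5 to 2 points the false-positive rate is 7% to 43%, always below one half, and no passage says which SD is ordinary. Nor do the documents support requiring a result to survive a fixed SD range. With 3 points as the upper end, an observed difference of about 9 points would be needed, against planned effects of 4 and 5. The comparison stays informative, but attributing it to the program is an assumption that the design cannot test.

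**What to change.** - **Protocol III.B:** add that the 80% power and 95% confidence are conditional on the two areas compared in each country, and do not cover area-to-area variation.
- **SAP A and E:** with each arm difference, report the break-even area SD, meaning the SD at which difference ± 1.96 × √(SE² + 2·SD²) first includes zero. Use a standard error that allows for clustering. If the interval already includes zero at SD 0, say that no break-even exists. Present this as a sensitivity analysis, not as a pass/fail rule.
- **Conclusions:** word each result as a difference between these two areas, and state attribution to the program as an assumption. Note that the areas were chosen purposively.

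The cost is a few sentences and a few lines of code, with no extra women, facilities or data. The downside is a less favourable precision statement and a more modest conclusion.
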